9. SECONDARY ENDPOINTS

9.1 Pregnancy Complications

Pregnancy complications will be summarized in tables by study arm and overall for each of the three cohorts, and by study arm and overall for the three cohorts combined. This analysis will include all participants in the analysis set who had an obtainable pregnancy outcome.

The summaries of complications will include the following complications, gathered on the Pregnancy Outcome CRF:

- any hypertensive disorders of pregnancy, and the different individual types of hypertensive disorders:
 - chronic
 - gestational
 - pre-eclampsia without severe features
 - pre-eclampsia with severe features
 - eclampsia
 - not specified
- chorioamnionitis
- either of puerperal sepsis or endometritis (combination of the puerperal sepsis and endometritis items), and summaries of both individually:
 - puerperal sepsis
 - endometritis
- either of peripartum and postpartum hemorrhage (Cohort 1 only)
- either of antepartum, intrapartum, or postpartum hemorrhage (Cohorts 2 and 3 only), and summaries of each type of hemorrhage individually:
 - peripartum hemorrhage (Cohort 1 only)
 - antepartum hemorrhage (Cohorts 2 and 3 only)
 - intrapartum hemorrhage (Cohorts 2 and 3 only)
 - postpartum hemorrhage
- preterm premature rupture of membranes (PROM) (the preterm premature rupture of membranes (PPROM) item)
- fever of unclear etiology
- other

The table will include a footnote listing the responses to "If 'Other', specify" for complications categorized as other. The number and percentage of participants, and the exact binomial confidence intervals for those proportions, with these complications will be summarized. The denominator will be the number of participants in the analysis set with a pregnancy outcome.

9.2 Infant Drug Levels

The number and percentage of infants with detectable drug levels in each study arm for each sample type will be summarized using descriptive statistics in tables overall for each of the three cohorts, and overall for the three cohorts combined. Participants with a drug level for the assay corresponding to their mother's randomization arm (i.e., plasma DPV concentration for the DPV VR arm, blood TFV-DP and FTC-TP concentration for the FTC/TDF arm) above the lower limit of quantification (LLOQ) at the PPO visit (including interim PPO visits) will be considered to have a detectable drug level for that sample type; otherwise, the participant will be considered to have an undetectable drug level for that sample type. If a participant has multiple concentrations at a visit, they will be considered to have a detectable drug level for that sample type if any of the concentrations are above the LLOQ. The denominator will be the number of infants in the analysis set with at least one valid drug result for the assay corresponding to their mother's randomization arm. Valid drug results are defined as any result that does not have any of the following censor codes: A, D, O, P, X, Z.

Additionally, drug concentration levels at the PPO visit (including interim PPO visits) will be summarized using geometric mean, geometric coefficient of variation (CV), arithmetic mean, standard deviation (SD), median, interquartile range (IQR), and range (minimum, maximum). The CV will be calculated as $100 \times$ standard deviation / Mean of the concentration values. Drug concentrations below the LLOQ will be treated as having a value of half the LLOQ for these summaries. Drug concentrations from assays that do not correspond to the mother's randomization arm, or which have any of the censor code A, D, O, P, X, and/or Z, will be excluded from these summaries.

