2.2 Study Objectives and Endpoints

Primary Objectives:

Maternal and Infant Safety: To describe the maternal and infant safety profile associated with

study product exposure during pregnancy

Pregnancy Outcomes: To describe the pregnancy outcomes associated with study product exposure during pregnancy

Primary Endpoints:

-

Maternal Safety (composite)

- All serious adverse events, including maternal deaths
- All Grade 3 or higher adverse events (AE) as defined by the Division of AIDS (DAIDS) Table for Grading the Severity of Adult and Pediatric Adverse Events, Corrected Version 2.1, July 2017 and/or Addendum 1 (Female Genital Grading Table for Use in Microbicide Studies [Dated November 2007])

Infant Safety (composite)

- All serious adverse events, including infant deaths and congenital anomalies
- All Grade 3 or higher AEs as defined by the Division of AIDS (DAIDS) Table for Grading the Severity of Adult and Pediatric Adverse Events, Corrected Version 2.1, July 2017

Pregnancy Outcomes

- Frequency of the following pregnancy outcomes:
 - Full term live birth (≥ 37 0/7 weeks)
 - Premature live birth (< 37 0/7 weeks)
 - Pregnancy loss (≥ 20 0/7 weeks)
 - Pregnancy loss (< 20 0/7 weeks)

Secondary Objectives:

Pregnancy Complications: To describe pregnancy complications associated with study product exposure during pregnancy

Infant Drug Levels: To describe infant levels of study drugs associated with study product exposure during pregnancy

Adherence: To characterize adherence to open label use of the DPV VR (25 mg) and oral Truvada in pregnant women

Acceptability: To characterize acceptability of open label use of the DPV VR (25 mg) and oral Truvada in pregnant women

Secondary Endpoints:

Pregnancy Complications

- Frequency of the following pregnancy complications:
 - Hypertensive disorders of pregnancy
 - Chorioamnionitis
 - Puerperal sepsis and endometritis
 - Antepartum, intrapartum and postpartum hemorrhage
 - Preterm premature rupture of membranes (PROM)
 - Fever of unclear etiology

Infant Drug Levels

- Infant blood tenofovir diphosphate (TFV-DP) and emtricitabine triphosphate (FTCTP) concentrations
- Infant plasma DPV concentrations

Adherence

- Maternal blood TFV-DP and FTC-TP concentrations
- Maternal plasma DPV concentrations
- Participant report of frequency of study product use (e.g., missed doses for oral Truvada and VR removal/expulsions [voluntary and involuntary] and duration without VR in vagina)

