- If sample was collected within 6 weeks (i.e., specimen collection date - randomization date + 1 day \leq 42 days):
Red (<150 fmol/punch)
Yellow (150 fmol/punch – 599 fmol/punch)
Green (\geq 600 fmol/punch)
- If sample was collected more than 6 weeks (i.e., specimen collection date – randomization date + 1 day $>$ 42 days) after randomization date:
Red (<200 fmol/punch)
Yellow (200 fmol/punch – 649 fmol/punch)
Green (\geq 650 fmol/punch)

Plasma DPV:

Red (<LLOQ (i.e., < 20 pg/mL))

Yellow (LLOQ – 95 pg/mL, inclusive)

Green ($>$ 95 pg/mL)

These categories will be summarized in terms of the number and percentage of participant visits, by visit (including all visits combined) and study arm for each of the three cohorts, and by visit and study arm for the three cohorts combined. The denominator will be the number of valid samples at the visit.

Adherence will also be summarized at a participant level for all three measures, with participants categorized as either “ever exposed” (if they have at least one measure in the Yellow or Green category) or “never exposed” (if they have no measures in the Yellow or Green categories). These categories will be summarized by number and percentage of participants by study arm for each of the three cohorts, and by study arm for the three cohorts combined. The denominator will be the number of participants with at least one valid sample.

Additional exploratory analyses of Blood TFV-DP categories may be done if additional information regarding adherence cutoffs becomes available. These exploratory analyses would not be part of the CSR.

Participant report of frequency of study product use will be summarized by visit for each of the three cohorts, and for the three cohorts combined. For participants randomized to the FTC/TDF arm this will be the responses to the “In the past 4 weeks, how often did you miss taking the pills” item on the Tablet Adherence CRF (possible responses are “never”, “rarely”, or “often”). For participants randomized to the DPV VR arm this will be the responses to the “in the past 4 weeks, how often was the ring out of your vagina for any extended period of time, that is more than 12 hours in a row?”, “in the past 4 weeks, how often was the ring out of your vagina, even for just a minute excluding expected instances when a ring was briefly removed and replaced with a new ring?”, and “was the ring ever removed (in the past 4 weeks)?” items on the Ring Adherence CRF.

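### SAP Section 9.2 names a geometric CV for infant drug concentrations but fixes the formula of the arithmetic CV

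*SAP*

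**What the plan says.** Infant drug levels are a secondary endpoint (SAP Section 2.2), including "Infant plasma DPV concentrations". Section 9.2 summarises the concentrations at the PPO visit by "geometric mean, geometric coefficient of variation (CV), arithmetic mean, standard deviation (SD"), followed by the median, IQR and range. The next sentence fixes the CV as 100 times "standard deviation / Mean of the concentration values". The same paragraph adds the substitution rule: "Drug concentrations below the LLOQ will be treated as having a value of half the LLOQ for these summaries".

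Nothing elsewhere in the SAP settles which CV is meant. The abbreviation list expands CV only as coefficient of variation. The general methods in Section 5 and the maternal adherence summaries in Section 9.3 list no CV. No log-scale formula for it appears anywhere.

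**The concern.** The name and the formula belong to different statistics. The geometric CV is built from the SD of the log concentrations and is the natural companion of the geometric mean. SD divided by mean on the raw scale is the arithmetic CV. Because the list holds one CV and attaches the abbreviation to the geometric one, the formula can only be read as its definition.

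Two things are at stake. A reader who meets a geometric CV beside a geometric mean will convert it back to a log-scale SD, for instance to compare studies, and that conversion would be wrong. The printed figure would also carry no new information, because the arithmetic mean and SD are already in the table and their ratio follows from them. The log-scale spread cannot be recovered exactly from the other statistics listed.

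**Working it through.** The SAP prints no CV value, so there is no figure to reproduce. The check compares the two formulas.

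**Formulas**
- Plan (Section 9.2): 100 × SD(x) / mean(x), with x the concentrations.
- Geometric CV: 100 × sqrt(exp(s²) − 1), with s = SD(ln x).

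**Inputs**
- From the SAP: substitution of half the LLOQ (Section 9.2), and planned group sizes of 50, 100 and 200 by arm and cohort, and 150 and 400 overall (Section 2.6, Table 1).
- Assumed, because the SAP does not give them: lognormal concentrations, log-SD from 0.5 to 1.5, and the share of infants below the LLOQ. The LLOQ is set at 20 pg/mL, the value in the maternal plasma DPV category of Section 9.3, "Red (<LLOQ (i.e., < 20 pg/mL". Both CVs are scale-free, so only the share below the LLOQ matters.

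**Step 1: hand example.** Take ten assumed values: 10, 10, 10, 25, 40, 60, 90, 150, 300, 900.
- Plan's formula: mean = 1595 / 10 = 159.5 and SD = 275.3, so 100 × 275.3 / 159.5 = 172.6%.
- Geometric CV: s = 1.5415, s² = 2.376, and 100 × sqrt(exp(2.376) − 1) = 312.5%.

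**Step 2: population values.** For an exactly lognormal variable the two formulas coincide:
- log-SD 0.5: 100 × sqrt(exp(0.25) − 1) = 53%
- log-SD 1: 100 × sqrt(exp(1) − 1) = 131%
- log-SD 1.5: 100 × sqrt(exp(2.25) − 1) = 291%

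**Step 3: samples with no values below the LLOQ.** Medians over several thousand simulated samples per setting, plan's formula against geometric CV. Repeat runs differ by a few points at most.

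| n | log-SD 0.5 | log-SD 1 | log-SD 1.5 |
|---|---|---|---|
| 50 | 51 vs 53 | 110 vs 129 | 177 vs 284 |
| 100 | 52 vs 53 | 116 vs 130 | 196 vs 288 |
| 400 | 53 vs 53 | 124 vs 131 | 228 vs 290 |

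**Step 4: samples with half-LLOQ substitution, n=100.**

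| Share below LLOQ | log-SD 1 | log-SD 1.5 |
|---|---|---|
| 10% | 117 vs 137 | 196 vs 283 |
| 30% | 118 vs 127 | 196 vs 225 |
| 50% | 118 vs 104 | 194 vs 163 |
| 60% | 114 vs 90 | 188 vs 133 |
| 80% | 95 vs 58 | 156 vs 77 |

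The plan's formula is below the geometric CV when few values fall under the LLOQ and above it when many do. Between these it can agree by coincidence: at n=400 with 30% below the LLOQ, 126 vs 127 at log-SD 1 and 226 vs 226 at log-SD 1.5. No fixed factor converts one into the other.

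**The case against.** The strongest reply is that this is a naming slip in one descriptive cell. The printed number would be a valid arithmetic CV, and a reader could recognise it from the SD and arithmetic mean in the same table. Intent is also unclear, so changing the label would remove the contradiction as well as changing the formula. All of this stands, and it sets the severity.

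A charitable reading of the formula as geometric SD over geometric mean does not help. The text refers to the concentration values. A geometric SD has no unit while a geometric mean does, so their ratio would change with the unit of measurement and is not the geometric CV. Reading the formula as an additional arithmetic CV fails too: none is listed, and the geometric CV would be left undefined.

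Four stronger inferences are tempting and not supported:

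- **That the reported spread of infant drug levels is wrong as a whole.** The SD, IQR and range are unaffected, as are the geometric mean, arithmetic mean, median and proportion with detectable drug.
- **That error limits around the geometric mean would be wrong.** Section 9.2 plans none, Section 3.2 makes the analyses descriptive unless otherwise noted, and nothing in the SAP takes the CV as an input.
- **That the formulas agree only in very large lognormal samples.** At log-SD 0.5 without censoring they differ by two points at n=50 (51 vs 53).
- **That the geometric formula is always closer to the underlying spread.** With 60% below the LLOQ at log-SD 1, neither 114% nor 90% recovers the uncensored 131%, and the plan's figure is the nearer. That distortion comes largely from the substitution rule, which correcting the CV formula does not change.

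**Conclusion.** The contradiction is real and lies within two consecutive sentences of Section 9.2: followed as written, the plan prints an arithmetic CV under the name of the geometric CV. The severity is minor, since one descriptive statistic of a secondary endpoint is mislabelled and no planned inference or decision depends on it.

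The mismatch itself rests on the text alone. Its numerical size rests on assumed lognormal data, log-SD and share below the LLOQ. Over the ranges examined it runs from negligible to more than 100 percentage points without censoring (177% against 284%, n=50, log-SD 1.5), and it changes sign under heavy half-LLOQ substitution. The largest gaps need a log-SD of 1.5 or a high share below the LLOQ, and the SAP gives no evidence on whether either will occur.

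**What to change.** Choose one of two changes in Section 9.2:

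- Keep the name and replace the formula: geometric CV = 100 × sqrt(exp(s²) − 1), where s is the SD of the natural-log concentrations after the stated half-LLOQ substitution.
- If SD over mean is what is intended, keep the formula and relabel the statistic as the arithmetic CV.

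The first adds information that the table otherwise lacks; the second only corrects the label. The first costs one SAP line and one line of code, the second a change of wording in the SAP and the table. Neither needs new data or alters any other planned summary.

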9.3 Adherence

Laboratory adherence measures (maternal blood TFV-DP and FTC-TP, maternal plasma DPV, and residual drug levels in VRs) will be summarized by visit for each of the three cohorts, and for the three cohorts combined. Residual drug levels in VRs will be reported in terms of the estimated residual drug release rate (see Appendix III for definition). Summaries will include the number of valid results, arithmetic mean, SD, median, IQR, and range.

Laboratory measures that do not correspond to the participant's randomization arm (i.e., maternal blood TFV-DP and/or FTC-TP for a participant randomized to receive the DPV VR, maternal plasma DPV and/or residual drug level in VRs for participants randomized to receive Truvada) will be excluded from all analyses described in this section. TFV-DP, FTC-TP, and plasma DPV measures that have any of the following censor codes will be excluded from all analyses described in this section: A, D, O, P, X, Z. Residual drug level measures that have the censor codes X or Z or for which residual drug release rate is unable to be calculated (see Appendix III) will also be excluded from all analyses described in this section.

By visit summaries will include the visits where the assessment was expected to be collected (e.g., mother blood TFV-DP and FTC-TP will include summaries for the time points where DBS for TFV-DP and FTC-TP drug levels were expected to be collected per protocol). Blood TFV-DP and plasma DPV samples that were collected at other visits will be treated as having been collected at the immediately preceding visit where collection was expected (e.g., a sample collected at an interim visit 4.1 will be treated as having been collected at visit 4). VRs that were returned at other visits will be treated as having been collected at the immediately following visit (see details below).

Residual drug levels in VRs visits

Visit 6 – Week 4: includes all rings returned on or prior to visit 6.0

Visit 10 – Week 8: includes all rings returned after visit 6.0 (i.e., visit 6.1 and later) and on or prior to visit 10.0

Visit 14 – Week 12, Visit 18 – Week 16, etc. are handled similarly.

Visit 101 – PPO Visit: includes all rings returned after last attended bi-weekly visit.

Laboratory adherence will also be categorized as follows:

Residual drug levels:

Red (rate \leq 0.9 mg/month)

Yellow (0.9 mg/month $<$ rate \leq 4.0 mg/month)

Green (rate $>$ 4.0 mg/month)

Blood TFV-DP:

- If sample was collected within 6 weeks (i.e., specimen collection date - randomization date + 1 day \leq 42 days):
Red (<150 fmol/punch)
Yellow (150 fmol/punch – 599 fmol/punch)
Green (\geq 600 fmol/punch)
- If sample was collected more than 6 weeks (i.e., specimen collection date – randomization date + 1 day $>$ 42 days) after randomization date:
Red (<200 fmol/punch)
Yellow (200 fmol/punch – 649 fmol/punch)
Green (\geq 650 fmol/punch)

Plasma DPV:

Red (<LLOQ (i.e., < 20 pg/mL))

Yellow (LLOQ – 95 pg/mL, inclusive)

Green ($>$ 95 pg/mL)

These categories will be summarized in terms of the number and percentage of participant visits, by visit (including all visits combined) and study arm for each of the three cohorts, and by visit and study arm for the three cohorts combined. The denominator will be the number of valid samples at the visit.

Adherence will also be summarized at a participant level for all three measures, with participants categorized as either “ever exposed” (if they have at least one measure in the Yellow or Green category) or “never exposed” (if they have no measures in the Yellow or Green categories). These categories will be summarized by number and percentage of participants by study arm for each of the three cohorts, and by study arm for the three cohorts combined. The denominator will be the number of participants with at least one valid sample.

Additional exploratory analyses of Blood TFV-DP categories may be done if additional information regarding adherence cutoffs becomes available. These exploratory analyses would not be part of the CSR.

Participant report of frequency of study product use will be summarized by visit for each of the three cohorts, and for the three cohorts combined. For participants randomized to the FTC/TDF arm this will be the responses to the “In the past 4 weeks, how often did you miss taking the pills” item on the Tablet Adherence CRF (possible responses are “never”, “rarely”, or “often”). For participants randomized to the DPV VR arm this will be the responses to the “in the past 4 weeks, how often was the ring out of your vagina for any extended period of time, that is more than 12 hours in a row?”, “in the past 4 weeks, how often was the ring out of your vagina, even for just a minute excluding expected instances when a ring was briefly removed and replaced with a new ring?”, and “was the ring ever removed (in the past 4 weeks)?” items on the Ring Adherence CRF.

9.4 Acceptability

Acceptability questions were asked of participants in Cohorts 2 and 3.

Self-reported attitude about study product and willingness to use study products during pregnancy will be assessed by summarizing the “would you be willing to use the [pills/ring] for HIV prevention when pregnant in the future?” item from the Follow-up Behavioral Assessment and Post-PO Behavioral Assessment CRFs. The responses from these two CRFs will be summarized separately for each of the visits where responses were expected to be collected (including interim visits for those expected visits): Visit 6 Follow-up Behavioral Assessment (both cohorts), Follow-up Behavioral Assessment from the 4-week Visit corresponding to, or immediately before, 36th week gestation (Cohort 3 only, see Section 3.2 Statistical Analysis Issues), and the Visit 103 6-week PPO Post-PO Behavioral Assessment, by study arm and overall for each of Cohorts 2 and 3. Responses at Visit 6 and Visit 103 will also be summarized by study arm and overall for these cohorts combined.

The proportion of participants who find the study products to be at least as acceptable as other HIV prevention methods will be assessed by summarizing the “overall, how much do you like or dislike male condoms for HIV prevention?”, “overall, how much do you like or dislike the [pills/ring] for HIV prevention?”, and “overall, how satisfied have you been with the [pills/ring] for preventing HIV?” items on the Follow-up Behavioral Assessment CRF. The responses from Visit 6 will be summarized by study arm and overall for each of Cohorts 2 and 3, and by study arm and overall for these cohorts combined. Responses from the 4-week Visit corresponding to, or immediately before, 36th week gestation (see Section 3.2 Statistical Analysis Issues) will be summarized by study arm and overall for Cohort 3. The denominator for each proportion will be the participants in the analysis set who responded to the item.

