- Residual drug levels in returned VRs

Acceptability

- Self-reported attitudes about study product attributes and willingness to use study products during pregnancy
- Proportion of participants who find the study products to be at least as acceptable as other HIV prevention methods

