5. GENERAL ANALYSIS METHODS

When the use of descriptive statistics to assess group characteristics or differences is described, the following methods will be used: for categorical variables, the number and percent in each category; for continuous variables, the mean, median, standard deviation, quartiles, and range (minimum, maximum).

Descriptions of tabular summaries that are “by study arm and overall” indicate that the table should have columns summarizing each arm as well as a column summarizing the combined arms.

Tabular summaries by visit do not include interim visits, unless otherwise noted. Results from all visits (including interim visits) will be included in listings.

[figure not shown]
In addition to separate analyses/summaries for each of the three cohorts, an exploratory analysis will split Cohort 3 participants into two groups based on gestational age (20 0/7 weeks through 29 6/7 weeks and 12 0/7 weeks through 19 6/7 weeks) as collected on the Pregnancy Assessment CRF. These ages were originally going to be two separate cohorts in Protocol Version 1.0 before being combined into one cohort in Protocol Version 2.0. These exploratory analyses splitting Cohort 3 will be done only for certain analyses, as specified in this document.

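### SAP section 9.4 gives no derivation for the comparative acceptability proportion, and the three separate item summaries it plans do not in general identify it

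*SAP*

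**What the plan says.** SAP section 2.2 lists two acceptability endpoints among the secondary endpoints. The second is: "Proportion of participants who find the study products to be at least as acceptable as other HIV prevention methods".

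Section 9.4 gives the planned analysis. The "proportion of participants who find the study products to be at least as acceptable as other HIV prevention methods will be assessed by summarizing" three items from the Follow-up Behavioral Assessment CRF:

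- Condom liking: "overall, how much do you like or dislike male condoms for HIV prevention"
- Product liking: "overall, how much do you like or dislike the [pills/ring] for HIV prevention"
- Product satisfaction: "overall, how satisfied have you been with the [pills/ring] for preventing HIV"

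Responses are summarised by study arm and overall. This is done at Visit 6 for Cohorts 2 and 3 and the two combined, and for Cohort 3 also at the 4-week visit at or just before gestational week 36. On denominators the section says: "The denominator for each proportion will be the participants in the analysis set who responded to the item".

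Section 5 sets what a descriptive summary contains: "for categorical variables, the number and percent in each category". For a continuous variable it is the mean, median, standard deviation, quartiles and range.

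**The concern.** The endpoint is a single proportion of women. Whether a woman counts depends on how her own view of the product compares with her own view of another method. The planned output is three one-variable tables. Nothing in section 9.4 says how two answers from the same woman are compared, which product item (liking or satisfaction) enters the comparison, how ties are handled, or who is in the denominator when one answer is missing.

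An analyst who follows section 9.4 exactly would produce tables from which the listed endpoint cannot in general be read. Either readers set the product percentage beside the condom percentage and infer a preference, or someone devises a rule later, in an open-label study, with the responses already in view.

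**Working it through.** The plan gives no figure for this endpoint, no response scale and no expected response rates, so there is nothing to reproduce. The check is whether the planned tables could still determine the endpoint.

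**1. Is there a paired rule elsewhere?** Section 5 defines only one-variable summaries, for categorical and continuous data alike. Section 9.4 sets the denominator item by item. Elsewhere the SAP does define participant-level variables when it wants them: detectable drug level (9.2), ever or never exposed (9.3), STI positivity over follow-up (10.8), and any abnormality on the Ages and Stages assessment (10.13). There is no equivalent for this endpoint.

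**2. What do the separate tables determine?** Let C be a woman's condom rating and P her product rating, on a common ordered scale with higher meaning better. The target is

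Pr(P ≥ C) = 1 − Pr(P < C),

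which depends on the joint distribution of P and C. Satisfaction concerns the product alone and adds nothing about C.

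**3. Two-level illustration (assumed inputs).** With like/dislike only, P < C means disliking the product and liking condoms. Let p be the share liking the product and c the share liking condoms. The joint probability lies between max(0, (1 − p) + c − 1) and min(1 − p, c).

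- p = c = 0.70: joint between max(0, 0.30 + 0.70 − 1) = 0 and min(0.30, 0.70) = 0.30, so the endpoint is **70% to 100%**.
- p = c = 0.50: joint between 0 and 0.50, so **50% to 100%**.
- p = 0.80, c = 0.60: joint between max(0, 0.20 + 0.60 − 1) = 0 and 0.20, so **80% to 100%**.
- p = c = 0.95: joint between 0 and 0.05, so **95% to 100%**.

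**4. Five-level illustration (assumed inputs).** For each level k, Pr(P ≥ C) is at least Pr(P ≥ k) + Pr(C ≤ k) − 1. The largest of these values is the lower bound, and it agrees with a linear-programming calculation.

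- Both items distributed 10/15/20/30/25% from worst to best: the values for k = 1 to 5 are 0.10, 0.15, 0.20, 0.55 + 0.75 − 1 = 0.30, and 0.25. The lower bound is 30%. The upper bound is 100%, reached if every woman gives both items the same rating. If the two ratings were independent, the figure would be 61%.
- Condoms as above, product 3/7/15/35/40%: the largest value is at k = 4, 0.75 + 0.75 − 1 = 0.50. The range is **50% to 100%**, with 75% under independence.

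The separate tables fix the endpoint only in special cases, such as every woman giving the product the top rating.

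**The case against.** A reader might infer that the endpoint will never be computed. The text does not support that. Section 9.4 names the proportion as its target, and both liking items sit on one CRF and are summarised at the same visits, so an analyst could derive it. What stands is that no derivation is written and the method that is written does not produce it.

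A reader might also infer that the condom and product percentages come from different women. Denominators can differ only through non-response to a single item, and nothing in the SAP suggests that this is material. The argument rests on marginal versus joint distributions, not on differing respondents.

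The ranges rest on chosen inputs. If nearly all women like the product, the two-level range is narrow, as the 95% case shows. That is fair: the figures show that the endpoint is not identified in principle, not how far off a report of this trial would be.

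The absence of a confidence interval is not part of the defect. The SAP calls for exact intervals for the primary endpoints and for pregnancy complications, but not for drug levels, adherence or acceptability, and its analyses are descriptive unless otherwise noted.

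Finally, comparing the liking ratings is one reasonable way to operationalise acceptability, not the only one. Section 9.4 also assigns the satisfaction item to this endpoint, so its role needs to be stated.

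**Conclusion.** The point holds as a gap in specification. Section 9.4 states a method, separate summaries of three items with item-level denominators, which does not in general estimate the within-woman proportion that section 2.2 lists. The illustrations give 70% to 100% on an assumed two-level scale with 70% liking each item, and 30% to 100% on an assumed five-level scale. They depend on assumed response distributions and should not be taken as the size of an error in this trial.

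A smaller point goes with it: the endpoint refers to other prevention methods in the plural, while the only alternative asked about in these items is the male condom. Section 9.4 makes that narrowing without saying so.

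The impact is limited to one descriptive secondary endpoint in Cohorts 2 and 3. No safety or pregnancy-outcome conclusion depends on it. The change is worth making because it is cheap and because a listed endpoint should have a defined result.

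**What to change.** Add a derivation to section 9.4:

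- Confirm on the CRF that the condom-liking and product-liking items use the same ordered response scale, and state its direction.
- Among women in the analysis set who answered both liking items at the same visit, set an indicator to 1 if the product rating equals or exceeds the condom rating, and to 0 otherwise.
- Report n/N and % by study arm and overall, at Visit 6 (Cohort 2, Cohort 3 and combined) and at the 36-week visit (Cohort 3). N is the number answering both items. An exact confidence interval is optional.
- Keep the three item tables, including satisfaction, as supportive, and say that this is their role.
- State that the comparator is male condoms only.

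The cost is a few lines of SAP text and one derived variable from data already collected. Women missing either item leave the denominator, so their number should be shown.
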